12.4.14 Change in Central Corneal Thickness

12.4.14.1 Statistical Hypotheses

[figure not shown]
No hypothesis testing of the endpoint is planned.

Document: TDOC-0056258 Version: 3.0; Most-Recent; Effective; CURRENT

Status: Effective Page 49 of 57

12.4.14.2 Analysis Methods

Change in central corneal thickness from baseline at each follow-up visits will be summarized. A mean, standard deviation, minimum, median, maximum, and a 95% confidence interval based on the t-distribution will be provided for the change and percentage change from baseline at each visit.

12.4.16 Comparison of COMPASS XXT Subjects to Original COMPASS Subjects Implanted with CyPass

Analysis will be conducted to compare subjects followed in this COMPASS XXT study to the full CyPass cohort implanted in the COMPASS trial.

ECD at baseline will be summarized for the two cohorts (COMPASS XXT vs. COMPASS). These summaries will include number of eyes, mean, standard deviation, and the following percentiles: 0th, 5th, 25th, 75th, 95th, and 100th.

Document: TDOC-0056258 Version: 3.0; Most-Recent; Effective; CURRENT

[figure not shown]
Status: Effective Page 50 of 57

The number and percent of eyes having ECD < 1000 will be reported for each cohort at 6 months and 24 months.

The within-eye ECD loss from baseline and % ECD loss from baseline at 6 months and 24 months will be summarized for the two cohorts. These summaries will include the number of eyes, mean, standard deviation, and the following percentiles: 0th, 5th, 25th, 75th, 95th, and 100th.

The within-eye ECD loss from 6 months to 24 months, and the % ECD loss from 6 months to 24 months will be summarized for the two cohorts. These summaries will include the number of eyes, mean, standard deviation, and the following percentiles: 0th, 5th, 25th, 75th, 95th, and 100th.

The number and percentage (specifying the denominator) of eyes with each level of observed rings at the 24-month visit will be reported for each cohort.

Document: TDOC-0056258 Version: 3.0; Most-Recent; Effective; CURRENT

Status: Effective Page 51 of 57

12.6 Interim Analyses and Reporting

Interim reports pertaining to the progress of the post-approval study will be submitted to the FDA for review every 6 months for the first 2 years and annually thereafter, starting from the date of FDA approval of the protocol, until study completion.

12.7 Handling of Missing Data

Missing data imputation will not be performed.

Document: TDOC-0056258 Version: 3.0; Most-Recent; Effective; CURRENT

Status: Effective Page 52 of 57

12.8 Sample Size Justification

Sample size (374) is based on the number of subjects who were implanted with a CyPass Micro-Stent in the COMPASS trial. It is not based on statistical power. 374 subjects were implanted with CyPass in the COMPASS trial. Of these, 215 volunteered to enroll in COMPASS XT. The total enrolled in this trial will be a subset of the 374 COMPASS CyPass subjects, is not restricted to those enrolled in COMPASS XT, and may be above or below the total enrolled in the COMPASS XT trial.

13 DATA HANDLING AND ADMINISTRATIVE REQUIREMENTS

13.1 Subject Confidentiality

The Investigator must ensure that the subject's anonymity is maintained throughout the course of the study. In particular, the Investigator must keep an enrollment log with confidential identifying information that corresponds to the subject numbers and initials of each study participant. At the end of the clinical study, the Study Sponsor will collect a copy of the enrollment log *without any identifying subject information*. All documents submitted to the Study Sponsor will identify the subjects exclusively by number and demographic information. No other personally identifying information will be transmitted to the Study Sponsor.

The Study Sponsor may release anonymized study data to external researchers for purposes of future research directly related to the study objectives, or future research that is beyond the scope of the current study objectives. The Informed Consent Form explains this to study subjects. Anonymization means that all identifiable information will be removed from the dataset and all links to the subjects in the study will be removed. Anonymization of the data will maintain confidentiality of the subjects who participate in the study so that they cannot be identified by external researchers. The anonymized data set will contain records from all of the subjects in the current study, but the anonymization process might change the data set in some ways, so external researchers will be informed that they might not be able to duplicate some of the results from this study.

13.2 Completion of Source Documents and Case Report Forms

The nature and location of all source documents will be identified to ensure that original data required to complete the CRFs exist and are accessible for verification by the site monitor, and all discrepancies shall be appropriately documented via the query resolution process. Site monitors are appointed by the Study Sponsor and are independent of study site staff.

Document: TDOC-0056258 Version: 3.0; Most-Recent; Effective; CURRENT

Status: Effective Page 53 of 57

If electronic records are maintained, the method of verification must be determined in advance of starting the study.

At a minimum, source documents include the following information for each subject:

- Subject identification (name, sex, race/ethnicity)
- Documentation of subject eligibility
- Date of informed consent
- Dates of visits
- Documentation that protocol specific procedures were performed
- Results of study parameters, as required by the protocol
- IP accountability records (if applicable)
- Documentation of AEs and other safety parameters (if applicable)
- Records regarding medical histories and the use of concomitant therapies prior to and during the study
- Date of study completion and reason for early discontinuation, if applicable

It is required that the author of an entry in the source documents be identifiable. Direct access to source documentation (medical records) must be allowed for the purpose of verifying that the data recorded on the CRF are consistent with the original source data.

Only designated individuals at the site will complete the CRFs. The CRFs must be completed at regular intervals following the clinical study visit schedule. It is expected that all data reported have corresponding entries in the source documents. The Principal Investigator is responsible for reviewing and certifying that the CRFs are accurate and complete. The only subject identifiers recorded on the CRFs will be subject number, and subject demographic information.

13.3 Data Review and Clarifications

A review of CRF data to the subject's source data will be completed by the site monitor to ensure completeness and accuracy. After the CRFs have been completed, additional data clarifications and/or additions may be needed as a result of the data cleaning process. Data clarifications are documented and are part of each subject's CRF.

Document: TDOC-0056258 Version: 3.0; Most-Recent; Effective; CURRENT

Status: Effective Page 54 of 57

13.4 Sponsor and Monitoring Responsibilities

The Study Sponsor will designate a monitor to conduct the appropriate site visits at the appropriate intervals according to the study monitoring plan. The clinical investigation will be monitored to ensure that the rights and well-being of the subjects are protected, the reported data are accurate, complete, and verifiable from the source documents, and the study is conducted in compliance with the current approved protocol (and amendments[s], if applicable), with current GCP, and with applicable regulatory requirements.

The site may not screen subjects or perform the informed consent process on any subject until it receives a notification from an appropriate Study Sponsor representative that the site may commence conducting study activities. Monitoring will be conducted periodically while the clinical study is ongoing. Monitoring methods may include site visits, telephone, written and fax correspondence. Close-out visits will take place after the last visit of the last subject at the site.

A Coordinating Investigator may be identified by the Study Sponsor to review and endorse the final study report. In cases where a Coordinating Investigator is engaged, the Study Sponsor will select the Coordinating Investigator based upon their experience, qualifications, active study participation, and their willingness and availability to take on this role.

13.5 Regulatory Documentation and Records Retention

The Investigator is required to maintain up-to-date, complete regulatory documentation as indicated by the Study Sponsor and the Investigator's files will be reviewed as part of the ongoing study monitoring. Financial information is to be kept separately.

Additionally, the Investigator must keep study records and source documents consistent with the terms of the clinical study agreement with the Study Sponsor. If the Investigator retires, relocates, or for any other reason withdraws from responsibility of keeping the study records, then the Study Sponsor must be notified and suitable arrangements made for retention of study records and source documents needed to comply with national and international regulations.

13.6 Quality Assurance and Quality Control

The Study Sponsor will secure agreement from all involved parties to ensure direct access to all study related sites, source data and documents, and reports for the purpose of monitoring and auditing by the Study Sponsor, and inspection by domestic and foreign regulatory authorities. Quality control will be applied to each stage of data handling to ensure that all

Document: TDOC-0056258 Version: 3.0; Most-Recent; Effective; CURRENT

Status: Effective Page 55 of 57

data are reliable and have been processed correctly. Agreements made by the Study Sponsor with the Investigator/Institution and any other parties involved in the clinical study will be provided in writing as part of the protocol or as a separate agreement.

14 ETHICS

This clinical study must be conducted in accordance with the ethical principles contained within:

- The Declaration of Helsinki, and in compliance with the ICH E6 GCP Consolidated Guideline, ISO 14155:2011, and the applicable US FDA 21 CFR Regulations.
- SOPs of the Study Sponsor and contract research organizations participating in the conduct of the clinical study and all other applicable regulations.
- Notifications and timelines for reporting protocol deviations should be based upon applicable Ethics Committee requirements

The Investigator must ensure that all personnel involved in the conduct of the study are qualified to perform their assigned responsibilities through relevant education, training, and experience. The Investigator and all clinical study staff must conduct the clinical study in compliance with the protocol. Deviations from this protocol, regulatory requirements and/or GCP must be recorded and reported to the Sponsor prior to database lock. If needed, corrective and preventive action should be identified, implemented, and documented within the study records. Use of waivers to deviate from the clinical protocol is prohibited.

Before clinical study initiation, this protocol, the informed consent form, any other written information given to subjects, and any advertisements planned for subject recruitment must be approved by an IRB/IEC. The Investigator must provide documentation of the IRB/IEC approval to the Study Sponsor. The approval must be dated and must identify the applicable protocol, amendments (if any), informed consent form, assent form (if any), all applicable recruiting materials, written information for subject, and subject compensation programs. The IRB/IEC must be provided with a copy of the Package Insert, any periodic safety updates, and all other information as required by local regulation and/or the IRB/IEC. At the end of the study, the Investigator must notify the IRB/IEC about the study's completion. The IRB/IEC also must be notified if the study is terminated prematurely. Finally, the Investigator must report to the IRB/IEC on the progress of the study at intervals stipulated by the IRB/IEC.

Voluntary informed consent must be obtained in writing from every subject and the process shall be documented before any procedure specific to the clinical investigation is applied to

Document: TDOC-0056258 Version: 3.0; Most-Recent; Effective; CURRENT

Status: Effective Page 56 of 57

the subject. The Investigator must have a defined process for obtaining consent. Specifically, the Investigator, or their delegate, must explain the clinical study to each potential subject and the subject must indicate voluntary consent by signing and dating the approved informed consent form. The subject must be provided an opportunity to ask questions of the Investigator, and if required by local regulation, other qualified personnel. The Investigator must provide the subject with a copy of the consent form written in a language the subject understands. The consent document must meet all applicable local laws and provide subjects with information regarding the purpose, procedures, requirements, and restrictions of the study, along with any known risks and potential benefits associated with the IP and the study, the available compensation, and the established provisions for maintaining confidentiality of personal, protected health information. Subjects will be told about the voluntary nature of participation in the study and must be provided with contact information for the appropriate individuals should questions or concerns arise during the study. The subject also must be told that their records may be accessed by appropriate authorities and Sponsor-designated personnel. The Investigator must keep the original, signed copy of the consent (file in subject's medical records) and must provide a duplicate copy to each subject according to local regulations.

The Study Sponsor assures that the key design elements of this protocol will be registered on www.clinicaltrials.gov as required by current regulations and, if applicable, other public databases as required by local country regulations. In addition, results of this study will be made publicly available on www.clinicaltrials.gov regardless of outcome as required by current regulations and, if applicable, in other public databases as required by local country regulations.

#### **Executive Summary:**

Key Objectives:

The primary objective is to assess long-term (10 years post-CyPass implantation) status of the corneal endothelium in subjects who were implanted with the CyPass Micro-Stent in the COMPASS trial.

### 1 Study Objectives and Design

### 1.1 Study Objectives

The objective of the study is to assess long-term (10 years post-CyPass implantation) status of the corneal endothelium in subjects who were implanted with the CyPass Micro-Stent in the COMPASS trial.

### **1.2 Study Description**

This is a prospective, non-interventional, observational, non-randomized, multicenter, single arm clinical study. Up to 374 subjects who were implanted with a CyPass Micro-Stent in the COMPASS trial will be enrolled. Subjects will be considered enrolled in the study after informed consent is obtained during the first study visit.

Subject participation in this study is variable depending on the number of follow-up visits expected. Annual follow-up visits will be scheduled for each subject based on the date of CyPass implantation and an exit visit will occur when the subject has reached 10 years post-CyPass implantation. For some subjects, the first visit will be at or after 10 years post-CyPass implantation, and therefore the first visit may coincide with the 120 Month/Exit visit.

The study is expected to be completed in approximately 4 years. Because collection of ECD is not part of standard of care, retrospective data collection will not be attempted for visits that occurred prior to subject enrollment. The one exception will be ocular adverse events data, which will be collected for all visits, wherever available.

### 1.3 Randomization

This study is not randomized, but the original COMPASS trial was randomized, and all subjects who are eligible for this trial were randomized to receive the CyPass device in the COMPASS trial.

### 1.4 Masking

Not Applicable

### 1.5 Interim Analysis

Interim reports pertaining to the progress of the post-approval study will be submitted to the FDA for review every 6 months for the first 2 years and annually thereafter, starting from the date of FDA approval of the protocol, until study completion.

### 2 Analysis Sets

### 2.1 Enrolled

The analysis set for both the safety and effectiveness analyses will be the set of all enrolled subjects. Only subjects enrolled in this study will be summarized.

### **3** Subject Characteristics and Study Conduct Summaries

Subject characteristics and study conduct summaries include tables and listings such as a subject disposition table, demographics table (including age, gender, and race). Counts and percentages will be presented for categorical variables such as sex, age, race, and study eye. Baseline ECD will be summarized overall with the mean, standard deviation, median, minimum, and maximum.

### 4 Safety Analysis Strategy

### 4.1 Safety Endpoints

The primary objective of the study is to assess long-term (10 year post CyPass implantation) status of the corneal endothelium in subjects who were implanted with the CyPass Micro-Stent in the COMPASS trial.

The safety endpoints are:

- Rate of occurrence of sight-threatening adverse events (AEs)
- Rate of occurrence of ocular AEs
- Central and peripheral (nasal) ECD measurements
- Analyses of rate of loss and rate of low ECD (ie,  $\leq 1000$  cells/mm2)
- Assessment of stabilization of ECL
- Corneal sequelae associated with ECL
- Association between peripheral and central ECD count and number of observed rings

• Secondary surgical interventions (SSIs) to modify the device position (eg, repositioning, trimming, explanation)

• Effects of SSIs on central and peripheral ECD

• CyPass Micro-Stent movement and/or malposition

• Corneal AEs (eg, corneal decompensation, tube corneal touch, corneal edema, etc.) caused by CyPass Micro-Stent

- Losses in Best Corrected Visual Acuity (BCVA) ≥10 letters
- Change in visual field mean deviation (MD)
- Change in central corneal thickness

### 4.2 Safety Hypotheses

There are no safety hypotheses planned in this study. The focus of the safety analysis will be to assess the long-term status of the corneal endothelium and a comprehensive descriptive assessment of occurrence of adverse events as well as the other listed parameters.

### 4.3 Statistical Methods for Safety Analyses

### 4.3.1 Rate of Occurrence of Sight-Threatening Adverse Events (AEs)

### 4.3.1.1 Statistical Hypotheses

No hypothesis testing of the endpoint is planned.

### 4.3.1.2 Analysis Methods

Descriptive statistics for sight-threatening adverse events will be presented for study eyes. The rates of all sight-threatening adverse events will be provided with counts and percentages, and these rates will be accompanied by two-sided exact 95% confidence intervals. An eye with multiple ocular adverse events of the same preferred term is only counted once toward the total of this preferred term. The list of adverse events which are considered to be sight-threatening can be found in Section 11.1.2 of the study protocol.

### 4.3.2 Rate of Occurrence of Ocular AEs

### 4.3.2.1 Statistical Hypotheses

No hypothesis testing of the endpoint is planned.

### 4.3.2.2 Analysis Methods

Descriptive statistics for ocular adverse events (including SSIs) will be presented for study eyes. The rates of all adverse events will be provided with counts and percentages, and these rates will be accompanied by two-sided exact 95% confidence intervals. An eye with multiple ocular adverse events of the same preferred term is only counted once toward the total of this preferred term.

### 4.3.3 Central and Peripheral (Nasal) ECD Measurements

### 4.3.3.1 Statistical Hypotheses

No hypothesis testing of the endpoint is planned.

### 4.3.3.2 Analysis Methods

Central and peripheral (nasal) endothelial cell density will be summarized at each visit. The number of eyes, mean, standard deviation, and the following percentiles will be reported: 0th, 5th, 25th, 75th, 95th, and 100th. A 95% confidence interval based on the t-distribution will be reported for the means at each visit.

The central endothelial cell coefficient of variation and hexagonality will be summarized by visit, in separate tables. The number of eyes, mean, standard deviation, and the following percentiles will be reported: 0th, 5th, 25th, 75th, 95th, and 100th.

# 4.3.4 Analyses of Rate of Loss and Rate of Low ECD (ie, ≤ 1000 cells/mm^2)

### 4.3.4.1 Statistical Hypotheses

No hypothesis testing of the endpoint is planned.

### 4.3.4.2 Analysis Methods

Change in central endothelial cell density (within-eye) from baseline and percent change in central endothelial cell density will be summarized by visit. Baseline central endothelial cell density is the data collected at the COMPASS Study baseline visit. All references to baseline endothelial cell density data throughout this protocol refer to data from this visit. The proportion of subjects with central endothelial cell density less than 1000 cells/mm^2, the proportion of subjects with peripheral cell density less than 1000 cells/mm^2, the proportion of subjects with central endothelial cell density less than 500 cells/mm^2, the proportion of subjects with peripheral cell density less than 500 cells/mm^2, the proportion of subjects with peripheral cell density less than 500 cells/mm^2, the proportion of subjects with peripheral cell density less than 500 cells/mm^2, the proportion of subjects with peripheral cell density less than 500 cells/mm^2, the proportion of subjects with peripheral cell density less than 500 cells/mm^2, the proportion of subjects with peripheral cell density less than 500 cells/mm^2, the proportion of subjects with peripheral cell density less than 500 cells/mm^2, the proportion of subjects with peripheral cell density less than 500 cells/mm^2, and the proportion of subjects

with central endothelial cell loss over 30% from baseline will also be reported at these time points. A 95% exact binomial confidence interval will be presented for the proportions. The following statistics will be presented for change in central endothelial cell density and percent change in central endothelial cell density at each visit: number of eyes, means, standard deviations, and the following percentiles: 0th, 5th, 25th, 75th, 95th, and 100th. A 95% confidence interval based on the t-distribution will be reported for the means at each visit. This analysis will be performed using central endothelial cell density data from visits in the COMPASS, COMPASS XT, and COMPASS XXT studies, where available, and using peripheral cell density data collected in this study. Summary statistics for peripheral (nasal) endothelial cell density will be presented for each study visit.

### 4.3.5 Assessment of Stabilization of ECL

### 4.3.5.1 Statistical Hypotheses

No hypothesis testing of the endpoint is planned.

### 4.3.5.2 Analysis Methods

The annualized rate of change and percent rate of change in central endothelial cell density will be summarized at each year of observation. A 95% confidence interval based on the t-distribution will be produced along with the mean, standard deviation, minimum, median and maximum. This analysis will be performed using central endothelial cell density data from visits in the COMPASS, COMPASS XT, and COMPASS XXT studies, where available.

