12.4.5.2 Analysis Methods

The annualized rate of change and percent rate of change in central endothelial cell density will be summarized at each year of observation. A 95% confidence interval based on the t-distribution will be produced along with the mean, standard deviation, minimum, median and maximum. This analysis will be performed using central endothelial cell density data from visits in the COMPASS, COMPASS XT, and COMPASS XXT studies, where available.

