### 4.5 Multiplicity Strategy

No statistical testing will be performed so no multiplicity adjustments are necessary.

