### 6 Handling of Missing Data

Missing data imputation will not be performed.

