### 7 Sample Size and Power Calculations

Sample size (374) is based on the number of subjects who were implanted with a CyPass Micro-Stent in the COMPASS trial. It is not based on statistical power. 374 subjects were implanted with CyPass in the COMPASS trial. Of these, 215 volunteered to enroll in COMPASS XT. The total enrolled in this trial will be a subset of the 374 COMPASS CyPass subjects, is not restricted to those enrolled in COMPASS XT, and may be above or below the total enrolled in the COMPASS XT trial.

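### Stabilization of endothelial cell loss is assessed only from separate yearly mean rates, with no within-eye estimate of the change in rate

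*SAP*

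**What the plan says.** "Assessment of Stabilization of ECL" is one of the listed safety endpoints in both documents. SAP 4.3.5.1 states "No hypothesis testing of the endpoint is planned". The planned method in SAP 4.3.5.2 is "The annualized rate of change and percent rate of change in central endothelial cell density will be summarized at each year of observation", and Protocol 12.4.5.2 is worded the same way, adding "A 95% confidence interval based on the t-distribution will be produced along with the mean, standard deviation, minimum, median and maximum". The data are central "density data from visits in the COMPASS, COMPASS XT, and COMPASS XXT studies, where available".

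Related statements:
- SAP 6: "Missing data imputation will not be performed".
- SAP 4.5: "No statistical testing will be performed so no multiplicity adjustments are necessary".
- SAP 7, on the 374 implanted subjects: "It is not based on statistical power". It adds that 215 of them joined COMPASS XT.

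Three other places come near this endpoint without covering it. SAP 4.3.4.2 summarizes change from the COMPASS baseline at each visit. SAP 4.7 summarizes 6-to-24-month loss, but to compare the COMPASS XXT cohort with the full CyPass cohort. Protocol 11.1.1 defines progressive ECL as an adverse event, and section 4.3.5 does not use that definition.

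**The concern.** Whether loss has stabilized has two parts: how large the late rate is, and whether it is lower than the earlier rate in the same eyes. The yearly tables address the first part one year at a time. They do not address the second. Anyone wanting it must compare row means, and the rows need not hold the same eyes.

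Three gaps add to this. The plan does not say whether an annualized rate runs between visits or cumulatively from baseline. It does not give the percent denominator. It does not say how the yearly intervals on two scales will be turned into a statement about stabilization. The study's stated objective is the status of the endothelium at 10 years, so this endpoint should be read from an estimate of the quantity it names.

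**Working it through.** The documents give no precision, threshold or expected rate for this endpoint, so there is no planned figure to reproduce. ECD level, loss, reading SD and number of eyes below are assumptions. Dates and head counts come from the documents.

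**1. Which eyes are in which row.**
- COMPASS followed subjects to 24 months and COMPASS XT to 60 months (Protocol 5.1). Of 374 subjects, 215 (57.5%) entered XT and 159 (42.5%) did not. Among subjects enrolled here, rows between 24 and 60 months can hold only the XT participants.
- No scheduled study visit falls between 60 and 84 months.
- The last COMPASS subject was randomized in March 2013. The earliest date in Protocol Table 7-1 is May 2020. The 84-month window closes at 2555 + 120 = 2675 days, and 1 May 2020 minus 2675 days is 3 January 2013. If visits begin in May 2020, and randomization stands in for implantation, only subjects treated from about January 2013 can have an in-window 84-month visit.
- Subjects whose first visit is the 120-month/exit visit give no annual rate within this study.

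Size of the effect, assuming that all 374 take part and every eye loses cells at a steady rate: if XT eyes lose 20 and the others 60 cells/mm² per year, an XT-only row shows 20 and a row with everyone shows 0.575 × 20 + 0.425 × 60 = 37.0. With the rates exchanged, the rows show 60 and 0.575 × 60 + 0.425 × 20 = 43.0. The row means move although no eye's rate has changed.

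**2. The interval for a difference cannot be recovered.** It depends on the between-year correlation ρ, which is not reported: half-width of the difference = yearly half-width × √(2(1 − ρ)), for the same eyes and equal SDs. With n = 100 and SD of annual change 150, the yearly half-width is 29.8. The difference then has a half-width of 51.6 (ρ = −0.5), 42.1 (ρ = 0) or 29.8 (ρ = 0.5).

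**3. A one-year interval against zero, if rates are visit-to-visit.** Take reading SD 100, n = 100 and no between-eye variation in slope.
- SD of a one-year change = √2 × 100 = 141.4; SE = 14.14.
- Half-width = 1.984 × 14.14 = 28.1 cells/mm² per year.
- P(interval includes zero), from the noncentral t distribution with noncentrality loss/14.14:

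| True loss per year | One given year | At least one of two consecutive years (simulated) |
|---|---|---|
| 20 | 0.71 | 0.97 |
| 30 | 0.44 | 0.77 |
| 50 | 0.06 | 0.12 |

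The result is just as sensitive to SD and n. At a loss of 30, the one-year probability is 0.07 with SD 75 and 150 eyes, and 0.77 with SD 150 and 75 eyes.

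**4. The two scales.** Take a constant 5% per year loss of the current count from 2400.
- Year 1 to 2: 2400 × 0.95 × 0.05 = 114.0.
- Year 9 to 10: 2400 × 0.95⁹ × 0.05 = 75.6.
- The absolute rate is 1 − 0.95⁸ = 34% lower (22% at 3% per year, 15% at 2%). Percent of the previous count stays at 5%.
- Percent of baseline falls from 114.0/2400 = 4.75% to 75.6/2400 = 3.15%, the same 34%, so there is no conflict.

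**5. Between-visit or cumulative rate.** Assume a 10% early drop from 2400, then a constant 50 per year. The rate annualized from baseline is (240 + 50t)/t: 290, 170, 98, 84 and 74 at years 1, 2, 5, 7 and 10. The between-visit rate after the early drop is 50 throughout. The cumulative version flattens by construction.

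**The case against.** The study is descriptive throughout. It plans no hypothesis test, makes no power claim and calls the endpoint an assessment. Stabilization can reasonably mean that the late rate is low, and a yearly rate with an interval estimates that directly. SAP 4.3.4.2 already gives change from baseline by visit, and SAP 4.7 already gives the early 6-to-24-month loss. All of this stands. It means that no test is missing and that the statement in SAP 4.5 is correct for a plan without tests.

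A reader might infer that the plan will declare stability when a late interval includes zero, or that its tables must support opposite verdicts for the same eyes. The documents do not support either inference. They state no such rule, and conflicting readings are possible, not certain. The probabilities in step 3 require visit-to-visit rates. If rates run from baseline, the year-10 half-width on the same inputs is 28.1/10 = 2.8, and an interval including zero at a true loss of 30 is practically excluded. A reader might also infer that the two scales necessarily disagree. That depends on the percent denominator, which is not stated.

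What the objection does not answer is that the rows can contain different eyes, and that no planned output estimates the change in rate within an eye.

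**Conclusion.** The concern holds in a limited form. The text in both documents supports yearly rates only. Row comparisons confound rate with composition, and the precision of a difference cannot be recovered. This follows from the wording and the visit history and needs no assumed ECD values.

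The numerical consequences are illustrations. The probability that a one-year interval includes zero runs from 0.71 to 0.06 as assumed loss goes from 20 to 50 cells/mm² per year (SD 100, 100 eyes), and it applies only to visit-to-visit rates. The 34% divergence between scales assumes 5% per year loss and a percent of current or previous count.

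This is a worthwhile, inexpensive improvement to a descriptive plan. It does not show that the planned summaries are invalid.

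**What to change.** In SAP 4.3.5.2 and Protocol 12.4.5.2:

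1. State that annualized rates are between visits, and give the percent denominator. Keep the by-year tables as supportive.
2. Add one table on log ECD, so that constant proportional loss gives zero difference. In the same eyes, report (a) the late annualized rate and (b) the late minus early (6 to 24 months) within-eye difference, each with n and a 95% t interval.
3. Fix the late window: 60 months to the last COMPASS XXT visit for eyes with a COMPASS XT 60-month reading. For eyes without one, use 24 months to the last XXT visit and report them separately, so that windows of different length are not pooled.
4. State that stabilization will be described from both estimates together, and that a single-year interval including zero is not by itself evidence of stabilization.

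No hypothesis test is needed, and SAP 4.5 can stand.

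As a rough guide on the cell scale (reading SD 100, 100 eyes, no between-eye slope variation), the half-width of the late-minus-early difference is:
- 60 to 120 months: 1.984 × 100 × √(2/1.5² + 2/5²)/10 = 19.5.
- 24 to 120 months, with a shared 24-month reading: 1.984 × 100 × √(2/1.5² + 2/8² + 2/(1.5 × 8))/10 = 20.7.

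A single one-year rate has 28.1. The gain comes from the longer intervals. Slope variation would widen the contrast, and these figures do not carry over directly to the log scale.

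The cost is a paragraph in each document and one table from data already in scope. Fewer eyes contribute, so n must be shown, and the late rate averages several years rather than isolating year 10.
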